#### **4.4 Aim 2: Adapted TranS-C versus Standard TranS-C on Fit to CMHC Context**

MLM will be used to account for multiple observations nested within Generation 2 providers. TranS-C treatment condition (Adapted versus Standard TranS-C) will be evaluated as a predictor of fit, operationalized as Generation 2 provider ratings of acceptability, feasibility, and appropriateness. The level 1 equation will include dummy-coded time indicators as the predictor (0 = post-training, 1 = post-treatment). The level 2 equation will include dummy-coded treatment condition (0 = Standard TranS-C, 1 = Adapted TranS-C) and treatment by time interaction terms as predictors, adjusting for county. The treatment effects of interest will be significant treatment by time interactions at the 5% level on the primary outcome of acceptability and the secondary outcomes of feasibility and appropriateness, all modeled as continuous variables. Significant treatment by time interactions indicate that change in perceptions of fit is significantly different comparing Adapted to Standard TranS-C. Significant interactions will be interpreted using planned contrasts (i.e., treatment effects on change from pre-treatment to post-treatment) and graphs.

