### Methods:

TTT will be implemented in nine CMHCs in California, United States (N = 60 providers; N = 130 patients) via facilitation. CMHCs are cluster-randomized by county to Adapted TranS-C or Standard TranS-C. Within each CMHC, patients are randomized to immediate TranS-C or usual care followed by delayed treatment with TranS-C (UC-DT). Aim 1 will assess the effectiveness of TranS-C (combined Adapted and Standard), compared to UC-DT, on improvements in sleep and circadian problems, functional impairment, and psychiatric symptoms for Generation 2 patients. Aim 2 will evaluate whether Adapted TranS-C is superior to Standard TranS-C with respect to Generation 2 providers' perceptions of fit. Aim 3 will evaluate whether Generation 2 providers' perceived fit mediates the relation between TranS-C treatment condition and patient outcomes. Exploratory analyses will: (1) evaluate whether the effectiveness of TranS-C for patient outcomes is moderated by generation, (2) compare Adapted and Standard TranS-C on patient perceptions of credibility/improvement and PhenX Toolkit outcomes (e.g., substance use, suicidality); and (3) evaluate other possible moderators.

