The first aim is to assess the effectiveness of TranS-C, compared to UC-DT, in patients who are treated by Generation 2 providers. We hypothesize that, compared to UC-DT, TranS-C (combined Adapted and Standard) will be associated with larger reductions in the primary patient outcome of sleep disturbance and the secondary patient outcomes of sleep-related impairment, functional impairment, and psychiatric symptoms. We also hypothesize that TranS-C’s benefits for functional impairment and psychiatric symptoms will be mediated by improvements in sleep and circadian problems. The second aim is to evaluate whether TranS-C treatment condition (Adapted vs. Standard TranS-C) is associated with fit to the CMHC context, operationalized as provider ratings of acceptability, appropriateness, and feasibility, for Generation 2 providers. We hypothesize that Adapted TranS-C will be superior to Standard TranS-C with respect to the primary provider outcome of acceptability and the secondary provider outcomes of appropriateness and feasibility. The third aim is to evaluate whether perceived fit among Generation 2 providers mediates the relation between TranS-C treatment condition and Generation 2 patient outcomes. We hypothesize that relative to Standard TranS-C, Adapted TranS-C will be associated with greater reductions in the primary and secondary patient outcomes indirectly through higher provider ratings of acceptability, appropriateness, and feasibility. Exploratory analyses will: (1) compare whether the effectiveness of TranS-C for primary and secondary patient outcomes is moderated by generation, (2) compare Adapted and Standard TranS-C on Generation 2 patient perceptions of credibility and perceived improvement and select PhenX Toolkit outcomes that are both strongly related to SMI and sleep and circadian problems (e.g., substance use, suicidality) (43–46) and of high priority to our community partners; and (3) determine whether treatment effects for Generation 2 patients are moderated by risk factors including age, sex, and sleep and circadian and psychiatric symptoms at baseline. In particular, emerging evidence suggests that patients who are older and have more severe sleep and circadian and psychiatric symptoms at baseline demonstrate poorer response to sleep and circadian treatment, whereas outcomes by sex have been mixed for patients with SMI (47,48).

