## **4 PLANNED ANALYSES**

### **4.1 Preliminary Analyses and Missing Data**

All analyses below pertain to the TTT Phase and are limited to Generation 2 providers and Generation 2 patients, except Exploratory Aim 1. For the primary analyses, which use multilevel modeling (MLM) and structural equation modeling, analyses will use all available data (intent-to-treat) (84). Models will be estimated with maximum likelihood estimation, and missing data will be assumed to be missing at random (85). For exploratory analyses using linear regression, approaches to missing data will be based on the number of missing cases (e.g., listwise deletion versus multiple imputation) (86). If dropout is related to other variables, they will be included as predictors. Baseline between-group differences in demographic variables will be examined. These tests will not be used to select covariates in the primary intention-to-treat analysis (87–90). Instead, covariates will be carefully selected at the conclusion of the trial—given the variations due to COVID-19 and the CMHC context (see Discussion)—and the potential influences of baseline differences will be evaluated as moderators (approach to moderation described below). Analyses comparing TranS-C to UC-DT will evaluate change in outcomes from pre-treatment to post-treatment. Analyses comparing Adapted to Standard TranS-C will evaluate change in Generation 2 outcomes from pre-treatment to post-treatment and pre-treatment to 6FU (see Method and Discussion for more details).

Distributions will be evaluated to detect outliers, and we will ensure that the assumptions of planned analyses are met. Covariates will include the patient variables for which we stratified (i.e., age and presence of psychosis or substance use). For all statistical models, counties will be adjusted for as a factor

variable rather than a level of analysis due to the relatively small number of clusters. The average intraclass correlation on provider and patient level outcomes will be reported.

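### Aim 2 tests only whether provider acceptability diverges after training; an Adapted–Standard gap already present by then cancels, and no level difference is planned or estimable

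*Combined protocol and SAP*

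**What the plan says.** The abstract states: "Aim 2 will evaluate whether Adapted TranS-C is superior to Standard TranS-C with respect to Generation 2" providers' perceptions of fit. Section 2 repeats it for the primary provider outcome: "We hypothesize that Adapted TranS-C will be superior to Standard TranS-C with respect to the primary provider outcome of acceptability". Neither sentence limits superiority to change.

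Section 4.4 opens by treating condition as a predictor of fit, then sets the coding: "The level 1 equation will include dummy-coded time indicators as the predictor (0 = post-training, 1 = post-treatment"). It names one effect: "The treatment effects of interest will be significant treatment by time interactions at the 5% level on the primary outcome of acceptability", with the two secondary fit measures handled the same way. It explains the result thus: "Significant treatment by time interactions indicate that change in perceptions of fit is significantly different comparing Adapted to Standard TranS-C". Contrasts and graphs follow a significant interaction, and the contrasts concern change.

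Section 4.1 also frames the version comparison as change: "Analyses comparing Adapted to Standard TranS-C will evaluate change in Generation 2 outcomes from pre-treatment to post-treatment and pre-treatment to 6FU". It adds: "For all statistical models, counties will be adjusted for as a factor" variable, because there are few clusters. The note to Table 2 says that the version is allocated by county and that providers enrol after training. Section 3.6.2 gives two provider assessments, after training and at post-treatment. Training takes 6–8 hours or two 3-hour blocks for Standard (section 3.4.1) and four hours in total for Adapted (section 3.4.2).

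**The concern.** In Aim 1, time 0 precedes treatment, so the difference in change carries the whole treatment effect. Aim 2 uses the same template, but its time 0 follows version-specific training and there is no earlier rating. The interaction therefore removes whatever effect the version has had by the end of training.

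A null or negative interaction could then be reported as Adapted not being superior on acceptability when Adapted was rated higher at both times. A positive interaction could be reported as superiority when Adapted had only caught up part of the way. In neither case would the planned output let a reader check.

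**Working it through.** **What the interaction measures.** Write A and S for the mean ratings under Adapted and Standard. The interaction is (A_post − A_training) − (S_post − S_training), that is, the post-treatment gap minus the post-training gap. In SD units:

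- 0.70 then 0.70: expected interaction 0
- 0.70 then 0.50: −0.20, although Adapted is higher at both times
- 0.35 then 0.70: +0.35
- 0 then 0.70: +0.70
- −0.70 then −0.35: +0.35, although Standard is higher at both times

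**Whether the model yields a level difference.** With this coding the condition term is nominally the post-training gap. The fixed part has an intercept, time, condition, condition × time and 8 county dummies: 12 columns. Condition is constant within county, so the rank is 11. The interaction is estimable; the condition difference at post-training or at post-treatment is not.

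**The plan's own figure.** Inputs from section 3.8: 60 providers, 9 clusters, ICC 0.20, coefficient of variation of cluster size 0.75, two-sided alpha 0.05, correlation between fit measures .83–.85 (0.84 used), stated minimum detectable d = 0.70. Assumed here: 80% power, equal arms, unit SD at both times, complete data.

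- Mean cluster size = 60/9 = 6.67
- Design effect = 1 + ((1 + 0.75²) × 6.67 − 1) × 0.20 = 2.883
- SE of the difference in change, providers independent = √(4 × 2 × (1 − 0.84)/60) = 0.146
- The same with the design effect = 0.146 × √2.883 = 0.248
- Minimum detectable difference = 2.80 × 0.248 = 0.69 (0.67–0.72 over the range of r), close to the stated 0.70; with SE 0.146 it would be 0.41

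**Power of the planned kind of test.** Section 4.4 has no term for county variation in change, so SE 0.146 applies if there is none. Two-sided normal power, with the range over r = .83–.85:

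- Difference −0.20: 28% (26–29%), almost all significant results favouring Standard
- Difference +0.35: 67% (64–70%)
- Difference +0.70: over 99%

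At SE 0.248 the powers are 13%, 29% and 81% (10.8%, 23% and 68% with t on 7 df). They describe a cluster-adjusted test of change. That test matches the stated 0.70, but it is not the model in section 4.4.

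**Precision of a level contrast.**

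- SE = √(4 × 2.883/60) = 0.438 SD
- 95% CI half-width = 1.96 × 0.438 = 0.86, or 2.365 × 0.438 = 1.04 with t on 7 df (9 counties minus 2)
- Minimum detectable difference = 2.80 × 0.438 = 1.23, or 1.43 from the noncentral t on 7 df

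**The case against.** The strongest reply is that Aim 2 means superior on change. Sections 4.1 and 4.4 plan change, section 3.11 describes the registered acceptability outcome as change, and the stated 0.70 is reproduced with a change-score variance. This stands in part: change is a legitimate, consistently planned estimand, and the case rests on an unqualified claim of superiority being wider than its test. The phrase "indirectly through higher provider ratings of acceptability, appropriateness, and feasibility" belongs to the Aim 3 hypothesis, so it supports a level reading of fit without settling what Aim 2 means.

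A second reply is that the gap should open in use. Staff in the earlier trial named dose and complexity as barriers (section 1), and providers are blind to version (section 3.2). If so, the planned test works. An early gap is also possible, since the trainings differ in length. The documents do not say which pattern to expect.

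A third is that other parts of the plan fill the hole. Section 3.8 promises to consider effect sizes for Aim 2, but names no level contrast. Aim 3 includes a path from condition to fit (sections 3.8 and 4.5), but does not define it as level or change, and it falls under the same county adjustment.

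A fourth is that the level contrast is too imprecise to settle anything. As a test, that is right: a true gap of 0.70 would give an interval excluding zero in only about 36% of trials (normal) or 28% (t, 7 df). It still shows direction and plausible range, which the interaction cannot.

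**Conclusion.** The point holds as a gap between the hypothesis and what the planned output can show. The cancellation and the aliasing are exact. The power figures depend on the assumptions listed and on no county variation in change. The harm depends on a pattern that the documents do not give.

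A reader might infer more, and three stronger readings are not supported:

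- That the interaction is the wrong test. It answers a legitimate question and detects a gap that opens during delivery.
- That a null or negative interaction carries no evidence against Adapted. It bears on change, and if there was no gap after training, a negative value means that Standard is rated higher at post-treatment. It is only insufficient by itself.
- That the planned model has the lower, cluster-adjusted powers. Those belong to another test. Inflated rejection when change varies by county is a separate issue.

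**What to change.** 1. Keep the interaction as the Aim 2 test, and state that it tests whether fit diverges between post-training and post-treatment. Add that by itself it neither establishes nor rules out a difference in level. A null or negative result is not enough to conclude that Adapted is not superior, a positive one is not enough to conclude that Adapted is rated higher, and either is to be read with the level estimates.
2. Whatever the interaction shows, report the Adapted–Standard difference in acceptability at post-training and at post-treatment with 95% CIs. Use a model with county as a random effect and small-sample degrees of freedom, or a county-level analysis with about 7 df. Make this an exception to the county rule in section 4.1 for this estimate only.
3. State its limits: the SE, CI half-width and minimum detectable difference shown above, possible imbalance across nine counties randomised without stratification, and selection because providers enrol after training. It is an estimate, not a test.
4. Log it in section 3.11 as a dated late addition, made before ratings are compared by version. Section 6 has assessments running through August 2023, and the research team knows each county's version (section 3.7).
5. In section 4.4, reconcile the contrast's starting point, given as pre-treatment, with the post-training coding. This may be loose wording for the same rating.

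The cost is low: one added model on ratings already collected, one narrow exception and a few sentences. The Aim 2 test and the parallel with the Implementation Phase are unchanged.

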#### **4.5 Aim 3: Fit as a Mediator of Treatment Condition and Patient Outcome**

Multilevel structural equation modeling (94) will be used to test whether improved perceptions of fit (i.e., acceptability, appropriateness, and feasibility) mediate the relation between TranS-C treatment condition (i.e., Adapted versus Standard TranS-C) and change in the primary patient outcome of sleep disturbance and the secondary patient outcomes of sleep-related impairment, functional impairment, and psychiatric symptoms in Generation 2. Models will evaluate change in outcomes from pre-treatment to post-treatment and pre-treatment to 6FU.

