(2017) application was conducted with 1,000 replications, 20,000 Monte Carlo draws per replication, and 95% confidence intervals (81). Drawing from prior research, medium correlations ( $r = 0.30$ ) were assumed between the predictor (TranS-C condition) and mediators (acceptability, appropriateness, feasibility; (80) as well as mediators and outcomes ( $r = 0.50$ ). Small correlations ( $r = .20$ ) were assumed between the predictor and outcomes (82). The power detected for the indirect effects with a sample size of  $N = 60$  providers (i.e., for the mediators) was 0.62. As with Aim 2, because we may be underpowered to detect statistical significance at alpha = 0.05, effect sizes will be considered in addition to p-values.

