The potential contributions of this protocol must be considered alongside its methodological limitations. First, given real-world factors, particularly the COVID-19 pandemic, our sample size is unlikely to be optimal and analyses may be underpowered. That said, estimates of the minimum detectable effect size presented above suggest that the anticipated sample sizes for providers and patients may be sufficient for Aim 1 and we will use effect sizes in conjunction with p-values to interpret the findings for Aims 2 and 3. Additionally, relative to the existing TTT literature in CMHCs, the current estimated sample for both providers and patients is substantial (8). Nonetheless, it is crucial for future research to examine TTT with larger samples to allow for more sophisticated analyses on the multitude of factors that may influence TTT outcomes.

Second, to reduce burden on our CMHC collaborators, we did not collect data from leadership nor local trainers at our partner CMHCs about their perceptions or feedback on TTT. We recognize that leadership-level factors can meaningfully impact implementation outcomes (104). Therefore, exploring leadership perspectives on TTT and TranS-C is an important direction for future research. Additionally, very few studies have collected data from local trainers (21). Thus, this area is ripe for both qualitative and quantitative research on a range of factors, such as local trainer attributes, effectiveness, competence, and perceptions of barriers and facilitators to sustaining the EBPT.

Third, as is common in TTT studies, our follow-up period is relatively brief (i.e., 6FU of TranS-C). It would be informative for future research to monitor outcomes over several generations of trainers and supervisors to provide robust tests of long-term TTT sustainability. Additionally, in the UC-DT condition, patients did not complete a 6FU assessment after the delay, and we did not collect 6FU data from providers. These were compromises made with CMHC partners to reduce burden and maximize participation in the study. Increasing our follow-up period to study the long-term effects of TranS-C relative to a control (e.g., UC-DT) and Generation 2 providers' perceptions of TranS-C will be important directions for future research.

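### Aim 3 implies up to 24 indirect effects, with no primary mediator-outcome-window combination, no error control, and no rule for how effect sizes bear on the conclusion

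*Combined protocol and SAP*

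**What the plan says.** Section 4.5 uses multilevel structural equation modelling to "test whether improved perceptions of fit (i.e., acceptability, appropriateness, and feasibility) mediate the relation between TranS-C treatment condition" and patient change. The outcomes are "change in the primary patient outcome of sleep disturbance" and "the secondary patient outcomes of sleep-related impairment, functional impairment, and psychiatric symptoms in Generation 2". On timing it says: "Models will evaluate change in outcomes from pre-treatment to post-treatment and pre-treatment to 6FU".

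Section 2 gives Aim 3 a directional hypothesis covering all three fit ratings and both the primary and the secondary patient outcomes. It lists the exploratory aims separately. Section 4.1 counts the multilevel and structural equation models among the primary analyses. For Aim 2, section 2 distinguishes the "primary provider outcome of acceptability and the secondary provider outcomes of appropriateness and feasibility". Sections 4.3 and 4.4 each state a 5% criterion for the effect of interest; section 4.5 states none.

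Section 3.8 reports power of 0.62 for the indirect effects with 60 providers, and adds: "because we may be underpowered to detect statistical significance at alpha = 0.05, effect sizes will be considered in addition to p-values". Section 5 repeats the intention: "we will use effect sizes in conjunction with p-values to interpret the findings for Aims 2 and 3". No multiplicity adjustment appears in section 4. Section 4.6 reruns Aims 1–3 in three sets of sensitivity analyses.

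**The concern.** Aim 3 is a hypothesised aim, yet the plan does not say which result would confirm it. Three ratings, four outcomes and two windows leave many routes to a significant indirect effect, and any of them could be reported as showing that fit mediates outcome. The case that matters most is the one where Aim 2's hypothesis is true and Aim 3's is false: Adapted TranS-C is better liked, but liking it does nothing for patients. The condition-to-fit path is then real for every rating, and each of the 24 tests needs only a chance association between fit and outcome. The intention to weigh effect sizes, with no interval or decision rule, leaves open how an imprecise estimate would be described.

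**Working it through.** **Inputs from the documents.** Mediators 3, outcomes 4, windows 2 (4.5). N = 60 providers, alpha 0.05, r = .30 condition–fit, r = .50 fit–outcome, r = .20 condition–outcome, stated power 0.62, from a run "conducted with 1,000 replications, 20,000 Monte Carlo draws per replication, and 95% confidence intervals" (3.8).

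**Inputs assumed.** The documents give no correlations among the fit ratings, among the outcomes or between windows. Ranges used: ratings 0–.85, outcomes 0–.7, windows 0–.8. A mid-range set was also used: ratings .6–.8, outcomes .3–.5, windows .5–.6.

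**1. The plan's own power.** The standardised paths are a = .30 and b = (.50 − .20 × .30)/(1 − .30²) = .44/.91 = .484, so ab = .145. Simulated power for one mediator and one unadjusted test is 0.633 when both paths must be significant by t test, and 0.641 with a Monte Carlo interval. A run of 1,000 replications has standard error √(.641 × .359/1000) = .015, so 0.62 lies (.641 − .62)/.015 = 1.4 standard errors from 0.641. The stated figure is therefore the power for a single path.

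**2. The count.** 3 × 4 × 2 = 24. With sleep disturbance only, 3 × 1 × 2 = 6. With fit as one construct, 1 × 4 × 2 = 8.

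**3. A crude reference.** If the 24 tests were independent at 5%, the chance of at least one would be 1 − .95²⁴ = 70.8%. This does not apply here: an indirect effect needs both paths, and the tests are correlated.

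**4. Chance of at least one significant indirect effect.** Each mediator has its own model, N = 60, single-level, two-sided. The 8-path column uses .5 for the outcome and window correlations.

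| True state | One named path | 8 paths | 24 paths |
|---|---|---|---|
| Neither path exists | 0.2% | 1.1% | 2–4% |
| Condition-to-fit null, fit related to outcome (r about .5) | 5.7% | 6.0% | 10–16% |
| Condition-to-fit r = .30, fit-to-outcome null | 3.7% | 18% | 24–55% |

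In the second row the inflation is modest because every outcome shares the same three condition-to-fit paths.

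**5. Narrower readings of the third row.**
- Mid-range correlations, all 24 paths: 32–43% two-sided, and 16–23% counting only the hypothesised direction (higher fit, greater reduction).
- Six sleep-disturbance paths: 10–18% over the full range of correlations. At mid-range they give 12–15%, or 6–7% in the hypothesised direction.
- Acceptability to sleep disturbance, both windows: about 6%.

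**6. Possible remedies.** One named path keeps the single-path power. Bonferroni over 24 paths brings the family rate in the third row to 1.3%, but cuts power for one path from 0.64 to 0.20 (0.35 at 0.05/6).

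**The case against.** Four points carry weight.

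First, the plan does label primaries: sleep disturbance within section 4.5 and acceptability in section 2. A reader might infer that Aim 3 has no primary outcome at all; the documents do not support that. What is missing is a statement that both labels carry into the mediation test, and a choice of window.

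Second, a reader might infer that mediation will be claimed falsely in a third or more of trials whatever the truth. That does not follow. The high rate needs a real effect on fit together with no effect of fit on patients, it includes wrong-direction results, and even then its lower end is 24%.

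Third, a reader might infer that a sizeable but non-significant estimate will count as support. The documents say only that effect sizes are considered alongside p-values because power may be low. They set no threshold and do not say that a non-significant estimate counts. The gap is the lack of a rule.

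Fourth, 24 is the upper reading. Section 4.5 does not say whether the ratings are modelled singly, jointly or as one construct, and the Aim 3 hypothesis in section 2 names no window. The simulation also omits the multilevel structure and the county term, so the rate under the planned model is unknown.

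These points lower the size of the problem and make it conditional. They do not supply the missing designation: even the 6-path and 8-path readings exceed the single-path rate severalfold in the scenario that matters.

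**Conclusion.** The concern stands in conditional form. Section 4.5 implies up to 24 indirect effects for a non-exploratory aim and leaves unstated the primary combination, the ranking of windows, any error control, and how effect sizes bear on the conclusion. At the protocol's own r = .30 for condition to fit, with fit unrelated to outcome, the chance of at least one false mediation finding is roughly 24–55%, against about 4% for one named path. In the other two null states it is 2–4% and 10–16%. The documents support neither an unconditional error rate nor the reading that effect sizes override p-values. The counts and the absence of a named path can be read directly from the plan. The percentages depend on correlations it does not give and on a single-level simulation, so they show an order of magnitude only.

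**What to change.** In section 4.5:

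- Name one confirmatory indirect effect that follows the plan's own primaries: condition to acceptability to PROMIS-SD, pre- to post-treatment. This keeps the single-path power of about 0.62 that section 3.8 reports.
- Label all other mediator-outcome-window paths secondary or supportive. Holm or false-discovery-rate adjustment of these is optional; Bonferroni across all 24 would cost too much power.
- State whether the three ratings are modelled singly, jointly or as one construct.
- Report each indirect effect with its 95% CI, and describe an estimate whose interval includes zero as inconclusive whatever its size. Refer to this rule where sections 3.8 and 5 mention effect sizes for Aim 3.

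The cost is a change of wording, and fewer paths can be claimed as confirmed. No new data or sample are needed.
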